Table 1. Clinical Laboratory Tests

Hematology	Clinical Chemistry	Urinalysis	Other Laboratory Tests
Hematocrit	Blood Urea Nitrogen (BUN)	Specific gravity	Serum pregnancy test
Hemoglobin	Creatinine	Ketones	Urine pregnancy test
Red Blood Cell (RBC) count	Total bilirubin	pH	HIV, if applicable (testing to be conducted at local lab)
White Blood Cell (WBC) count	Albumin	Protein	HBsAg
Neutrophils	Aspartate aminotransferase (AST)	Glucose	HBsAb
Bands	Alanine aminotransferase (ALT)	Blood	HBcAb
Lymphocytes	Alkaline phosphatase	Leukocytes	HBV PCR
Monocytes	Sodium	Nitrites	HCV PCR
Basophils	Potassium		PPD or the QuantiFERON-TB Gold test
Eosinophils	Chloride		hs-CRP
Platelet count (estimate not acceptable)	Calcium		FSH*
	Inorganic phosphorus		
	Uric acid		
	Cholesterol		
	Total protein		
	Glucose		
	Triglycerides		
	Sodium bicarbonate		

* If applicable.

Assessment of Peripheral Joints

Tender Joint Count (TJC) and Swollen Joint Count

(SJC)

TJC68 and SJC66, including the DIP joints of the hands and excluding hips for swelling, will be performed as recommended for clinical trials in PsA.⁴¹ Additionally, the TJC28 and SJC28 required for the calculation of DAS28 will be extracted from the corresponding TJC68 and SJC66, respectively. The TJC/SJC assessments will be performed at the visits specified in [Appendix C](#).

Tender Joint Count (TJC)

An assessment of 68 joints (TJC68; [Appendix E](#)) will be done for tenderness by pressure manipulation on physical examination. Joint pain/tenderness will be classified as either present ("1"), absent ("0"), replaced ("9") or no assessment ("NA").

Swollen Joint Count (SJC)

An assessment of 66 joints (SJC66; [Appendix E](#)) will be done by physical examination. The joints to be examined for swelling are the same as those examined for tenderness, except the hip joints excluded. Joint swelling will be classified as present ("1"), absent ("0"), replaced ("9") or no assessment ("NA").

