If possible, the TJC and SJC should be performed by an **independent joint assessor** who should not perform any other study related procedures, as much as possible. In order to minimize variability, the same joint assessor should evaluate a subject at each visit throughout the duration of the trial. A back-up independent assessor, who is trained and competent in performing such assessments, should be identified. It is the responsibility of the Principal Investigator to ensure all assessors are qualified to perform joint assessments. If the independent assessor is not available, the pre-identified back-up assessor will perform such assessments.

Dactylitis Assessment

Dactylitis will be assessed as dactylitic digit count and tender dactylitic digit count.

Hands and feet bilaterally will be assessed for the presence/absence of dactylitis and associated tenderness. The score for each dactylitic count and tender dactylitic count can range 0-20 ([Appendix F](#)). The dactylitis assessments will be performed at the visits specified in [Appendix C](#).

Enthesitis Assessment

Leeds Enthesitis Index (LEI)

The LEI⁴² is an enthesitis measure developed specifically for PsA and assesses the presence or absence of tenderness at the following 3 bilateral enthesial sites: medial femoral condyles, lateral epicondyles of the humerus, and Achilles tendon insertions. Tenderness on examination is recorded as either present (1) or absent (0) for each of the 6 sites, for an overall score range of 0-6 ([Appendix G](#)). The LEI assessments will be performed at the visits specified in [Appendix C](#).

Tenderness at the Plantar Fascia

Tenderness at the plantar fascia as an additional typical PsA enthesitis site²⁷ will be assessed as present (1) or absent (0) ([Appendix G](#)). The tenderness at the plantar fascia assessment will be performed at the visits specified in [Appendix C](#).

Psoriasis Evaluation

Psoriasis Area and Severity Index (PASI)

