Patient's Global Assessment of Arthritis will be performed on a 100 mm horizontal VAS with a question referring to arthritis disease activity over the past week.⁴⁶ The VAS is anchored by the opposite adjectives of "excellent" and "poor."

Patient's Assessment of Pain

Patient's Assessment of Pain will be performed on a 100 mm horizontal VAS with a question referring to pain over the past week.⁴⁶ The VAS anchors are "no pain" and "pain as bad as it could be."

Psoriatic Arthritis Impact of Disease (PsAID)

PsAID is a validated patient self-reported tool to assess the impact of PsA on patient's life. Two versions of the questionnaire were developed by an European League Against Rheumatism (EULAR) initiative: one for clinical practice (PsAID-12) and one for clinical trials (PsAID-9). Both contain physical and psychological domains. The PsAID-9 version will be used in this study.⁴⁷

Health Assessment Questionnaire Disability Index (HAQ-DI)

The HAQ-DI is a standardized measure of physical function in arthritis. The HAQ-DI questionnaire contains 20 items divided into 8 domains that measure: dressing and grooming, arising, eating, walking, hygiene, reach, grip, and common daily activities.⁴⁸

Short Form 36 Health Survey (SF-36)

SF-36 is a generic measure to assess patients' general health and well-being (i.e., health related quality of life). The short version 2 (SF-36v2) consisting of 36 questions will be used.^{49,50}

Dermatology Life Quality Index (DLQI)

DLQI is a measure of subject's quality of life (QoL) related to skin disease. The DLQI questionnaire consists of 10 questions concerning subjects' perception of the impact of skin diseases on different aspects of their health related quality of life over the last week. The items of the DLQI encompass aspects such as symptoms and feelings, daily activities, leisure, work or school, personal relationships and the side effects of treatment.⁵¹

Self-Assessment Psoriasis Symptoms (SAPS) v.3.0

The subject will rate his/her psoriasis symptoms within the past 24 hours utilizing an 11-item questionnaire.⁵²

Musculoskeletal Ultrasound (US)

Investigators will at study start indicate if they want to participate in the optional US assessments or not. If they decide to participate, they should, if possible, perform an US evaluation for every subject they enroll at visits indicated in [Appendix C](#).

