For the sites participating in the optional US assessment, high-end ultrasound equipment is recommended. The US must be performed by an expert sonographer (rheumatologist or radiologist) with verifiable training and/or certification in ultrasonography, and at least 3 years of regular US experience. Prior experience in multicenter ultrasound study(ies) is recommended, otherwise training will be provided. The Ultrasonographer must be independent of the clinical Investigator and should be blinded for subject characteristics and treatment arm; he/she should be the same person throughout the study, and a back-up with the same qualifications should be appointed.

The assessments and scoring will be locally performed. US should be performed the same day as the clinical examination, or the day before the visit if not possible, and prior to injecting study medication. The subjects undergoing US evaluation should not take NSAIDs for the last 48 hours prior to the US assessment. (See Section [5.2.3.2 Prohibited Therapy](#)).

The ultrasound evaluation will comprise a comprehensive assessment of joints, entheses and tendons.

For the joint evaluation, the following 23 pairs of joints will be scanned:

- Metacarpophalangeal (MCP) joints 1 to 5,
- Proximal interphalangeal (PIP) joints 1 to 5,
- Distal interphalangeal (DIP) joints 2 to 5,

- Metatarsophalangeal (MTP) joints 1 to 5,
- Wrist, elbow, knee, ankle (tibiotalar).

The US assessment of synovitis will consist of an evaluation of hypoechoic synovial hyperplasia (SH) using Grayscale (or B mode) and synovial vascularization using Power Doppler (PDUS). The pre-specified set of 23 paired joints will be scanned in longitudinal and transverse scan from the dorsal aspect with the joint in a neutral position, except for the knee, which will also be examined in a flexed position (30°).

The presence of synovitis (i.e., SH and Power Doppler) will be scored according to the OMERACT-EULAR PDUS composite semi-quantitative scale (0 to 3).⁵³

For the entheses evaluation, the following 5 pairs of entheses will be scanned:

1. Common extensor tendon insertion at the lateral humeral epicondyle,
2. Quadriceps tendon insertion at the superior pole of the patella,
3. Patellar tendon proximal insertion at the inferior pole of the patella,
4. Patellar tendon distal insertion at the tibia tuberosity,
5. Achilles tendon insertion at the calcaneus; plantar aponeuroses insertion at the calcaneus.

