5.3.3 Efficacy Variables

5.3.3.1 Primary Variable

The proportion of subjects in MDA at Week 16 on adalimumab 40 mg eow plus MTX 15 mg ew as compared with subjects on MTX alone escalated to 20- 25 mg or highest tolerable dose ew.

Minimal Disease Activity (MDA)

MDA in PsA is defined as fulfilling at least 5 of the 7 following criteria:^{57,58}

- TJC \leq 1 (out of TJC68 assessed in this study)

- SJC ≤ 1 (out of SJC66 assessed in this study)
- PASI ≤ 1 or BSA ≤ 3
- Patient's assessment of pain VAS ≤ 15
- Patient's global assessment of disease activity (PtGA) VAS ≤ 20
- HAQ-DI score ≤ 0.5
- Tender enthesal points ≤ 1 (out of 8 assessed in this study)

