5.5.3 Method of Assigning Subjects to Treatment Groups

All subjects will be centrally randomized using IRT. Before the study is initiated, IRT directions will be provided to each site.

All subjects will be assigned a unique identification number by the IRT at the Screening visit. Subjects who meet the inclusion and exclusion criteria defined in Section 5.2.1 and Section 5.2.2 will be centrally randomized in a 1:1 ratio to adalimumab + MTX or MTX alone on Day 1 (Baseline). Using IRT, subjects will be first stratified by the duration of MTX treatment at 15 mg ew into two strata: ≤ 3 months and > 3 months. Then within each stratum, the IRT will assign a randomization number that will encode the subject's

treatment group assignment according to the randomization schedule generated by the Statistics Department at AbbVie.

After the assessment of MDA at Week 16, subjects will be assigned to one of the four treatment arms of Part 2 (Arms 1-4) as described in Section 5.1 for an additional 16 weeks using IRT. Additionally, IRT will be used to dispense study medication if a subject changes the mode of MTX administration (i.e., oral to sc or sc to oral) and if applicable decreases the dose of MTX (e.g., change from 25 mg sc to 20 mg sc or change from 20 mg sc to 15 mg sc). The sites will register changes in dose and mode of administration into IRT.

IRT will provide the appropriate medication kit number(s) to dispense to each subject. Study drug will be administered at the study visits as summarized in [Appendix C](#). Returned study medication should not be re-dispensed to any subject.

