5.5.5 Blinding

This study is open-label study. Blinding is not applicable.

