For the enthesis evaluation, US will be initially performed in B mode to detect morphologic abnormalities, and subsequently with power Doppler to detect abnormal vascularization at bony insertion. For each enthesis the following elementary lesions will be recorded within 2 mm from the cortical bone, according to the OMERACT definition of enthesitis:⁵⁵

- Presence of Doppler signal,
- Hypoechoogenicity of the tendon insertion,
- Thickening of tendon insertion,
- Erosions,
- Enthesophytes,
- Calcifications.

Except for the presence of Doppler signal, each elementary lesion will be scored binary as present or absent. The presence of Doppler signal will be scored semiquantitative as 0 (absent) to 3 (severe), according to the following semi-quantitative grade:

- 0 = absent
- 1 = maximum 3 Doppler spots,
- 2 = more than 3 and less than 50% of the enthesis area
- 3 = more than 50% of the enthesis area

Tenosynovitis Evaluation

The following 14 tendon compartments will be assessed bilaterally for the presence of GS and Doppler tenosynovitis:

- Extensor compartments at the wrist (1 to 6),
- 2nd-5th finger flexor tendons,
- Tibialis posterior, flexor hallucis longus, flexor digitorum common and peroneal tendons.

Presence and grading of tenosynovitis will be defined and performed according to the OMERACT definition and scoring system.⁵⁶

Note: Standardized evaluation scans and examples of synovitis, enthesitis and tenosynovitis grading for each site examined will be available in an Atlas.

Technical Requirements:

Different models of ultrasound machines are allowed as long as B-mode (Greyscale) and high quality Doppler modules are available. It is recommended to use high-end machines as per the training Atlas which will be provided. B-mode and Doppler machine settings will be optimized before the study and standardized for the whole study.

US Assessment Conditions:

The US assessments must be performed by an expert in musculoskeletal US with verifiable training and/or certification and at least 3 years of experience. Ideally, the ultrasonographer should have prior experience in multicenter study(ies); otherwise training will be provided. The Ultrasonographer must be independent of the clinical Investigator and should be blinded for subject characteristics and treatment arm; he/she should be the same person throughout the study, and a back-up with the same qualifications should be appointed. The clinical assessor will be blinded to the US scoring.

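### The independent joint assessor, who rates two of the seven items of the primary endpoint, is not asked to be blinded to treatment arm, although the ultrasonographer for an optional exploratory measure is

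*Protocol*

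**What the plan says.** **Joint counts.** Protocol 5.3.1.1 (Swollen Joint Count) wants both counts done by an independent assessor if possible, "who should not perform any other study related procedures, as much as possible". The same person should examine a subject at every visit, and the reason given is variability. A trained back-up is to be named. Blinding to arm is not mentioned for either person.

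**Ultrasound.** The same section is explicit for the other rater: "The Ultrasonographer must be independent of the clinical Investigator and should be blinded for subject characteristics and treatment arm". Appendix J repeats this. Sites choose whether to take part ("Investigators will at study start indicate if they want to participate in the optional US assessments or not"), and the ultrasound scores are exploratory (Protocol 5.3.3.3, SAP 4.3.3). Appendix J also says "The clinical assessor will be blinded to the US scoring", which concerns ultrasound results and not treatment.

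**Study level.** Protocol 5.5.5 reads: "This study is open-label study. Blinding is not applicable". Section 5.6.1 gives the reason for the open-label design: subcutaneous as well as oral methotrexate had to be possible.

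**Primary endpoint.** Protocol 5.3.3.1: "MDA in PsA is defined as fulfilling at least 5 of the 7 following criteria". Two of the seven are a tender count of at most 1 of 68 and a swollen count of at most 1 of 66. SAP 6.2 tests Week 16 MDA with a stratified Cochran-Mantel-Haenszel (CMH) test under non-responder imputation, and repeats it on observed cases.

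**The concern.** Independence separates the joint examiner from other study tasks. It does not stop that person from knowing the arm. An examiner who knows it may, without intending to, call a borderline joint differently in the two arms, and the cut-off of one joint leaves little slack. The effect could favour either arm.

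The protocol's own ultrasound rule shows that the sponsor regards an arm-blinded rater as workable in this trial. Allowing two routes of methotrexate is a reason not to blind subjects and prescribers. It does not prevent blinding an examiner who does little else.

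The observed-cases analysis cannot reveal such a bias, because it changes the handling of missing data and keeps the same ratings. Two planned outputs are partial checks. The summary of each MDA component by arm (SAP 6.4) could show the swollen-joint item departing from the others, but a true effect on joints would look the same. The Week 16 ultrasound comparison has a rater who should be blinded, but only at participating sites and on a different measure. Neither corrects the primary endpoint. The joint counts also enter PASDAS, DAPSA, ACR response and DAS28-CRP (Protocol 5.3.3.2).

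**Working it through.** **1. The plan's own figure.** Inputs (Protocol 8.2, SAP 4.4): MDA 40% v 20%, two-sided 0.05, at least 90% power, about 10% dropout. The two-proportion formula with pooled variance and no continuity correction gives 109 per arm. Then 109 × 1.10 = 119.9, so 120 per arm and 240 in total, as stated. (Dividing instead, 109 / 0.90 = 121.1, gives 122 per arm.) Blinding the joint assessor changes none of these inputs.

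**2. Who is asked to be blinded to what.**

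| Rater | Measure | Independent? | Blinded to arm? |
|---|---|---|---|
| Joint assessor and back-up | Two primary-endpoint items | If possible | Not asked |
| Ultrasonographer | Optional, exploratory | Required | Asked |
| Clinical assessor (Appendix J) | Clinical examination | Not stated there | Not asked; blinded to ultrasound scores only |

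**3. When one joint matters.** A one-joint difference in the swollen count changes MDA only at the cut-off: exactly five items met with a count of 1 (a responder can be lost), or exactly four met with a count of 2 (a responder can be gained).

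**4. Illustration of size.** The documents give neither the share of subjects at the cut-off nor a misrating rate, so both are assumed:
- s = share of true responders at the swollen-joint cut-off: 10%, 20% or 30%.
- q = probability that such a subject is rated one joint higher: 10%, 25% or 50%.
- True MDA is 20% in both arms, 120 per arm, so 0.20 × 120 = 24 responders per arm.
- Misrating occurs in the methotrexate arm only.

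Observed methotrexate rate = 0.20 × (1 − s × q). In the central case this is 0.20 × (1 − 0.20 × 0.25) = 0.19. That is 1.0 point, or 24 × 0.05 = 1.2 subjects.

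The rejection probability is the exact sum over two binomials of size 120. The statistic is the single-stratum CMH chi-square without continuity correction, rejecting above 3.841. With no misrating it is 5.1%.

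| s | q = 10% | q = 25% | q = 50% |
|---|---|---|---|
| 10% | 5.1% | 5.2% | 5.6% |
| 20% | 5.2% | **5.6%** | 6.9% |
| 30% | 5.3% | 6.1% | 9.4% |

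Seven of the nine cells lie between 5.1% and 6.1%. The corner of 9.4% corresponds to 24 × 0.30 × 0.50 = 3.6 subjects, or 3.0 points.

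**5. Bias the other way.** At the planned 40% v 20%, exact power is 92.9%. With the central misrating in the adalimumab arm only, the rates are 0.40 × 0.95 = 0.38 v 0.20 and power is 87.4% (extreme corner 69.1%). With equal misrating in both arms, 0.38 v 0.19, power is 91.1%.

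Only downgrades of the swollen count are modelled. Upgrades, and the tender count, are not.

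**The case against.** The strongest reply is that this is a declared, pragmatic open-label trial with a stated reason, and nothing in it promises a blinded joint examiner. The protocol chose its own safeguards: an independent assessor, the same one throughout, a trained back-up, and questionnaires completed before any examination or contact with site staff. That stands. Nothing is broken, and the point is an improvement.

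Three stronger readings are tempting, and the documents do not support them.

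- *A reader might infer that the swollen count is the item most exposed to examiner bias.* Tenderness is assessed by pressure ("will be done for tenderness by pressure manipulation on physical examination"), so it depends on the open-label subject too. That separates swelling from tenderness only. PASI and BSA also form an MDA item, are rated by the investigator or a delegate, and have no independent assessor at all. The swollen count is the better protected of the two.
- *A reader might infer that section 5.5.5 contradicts the ultrasonographer rule.* It sits under Treatments and can be read as saying that treatment is not blinded. A masked rater in an optional assessment is compatible with that. The wording needs clarifying, no more.
- *A reader might take 9.4%, or power of 69.1%, as the expected damage.* Both come from one corner of an assumed grid, with one-directional misrating in a single arm. They do not show that such bias is likely.

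The remedy is also narrow. Five of the seven items are untouched, three of them reported by unblinded subjects.

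**Conclusion.** The gap is real on the text: arm-blinding is asked of the rater of an optional exploratory measure and not of the rater of two primary-endpoint items, although the second role already exists. Closing it would reduce one source of bias in the primary endpoint without removing the others.

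The size cannot be derived from the documents. Under the assumed central case the cost is about half a point of type I error (5.1% to 5.6%). Substantially more needs both a large share of responders at the cut-off and frequent misrating confined to one arm. The point is worth considering for its low cost. It does not undermine the design or the sample size.

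**What to change.** 1. In Protocol 5.3.1.1, state that the independent joint assessor and back-up, where available, should be blinded to treatment arm, and that subjects are asked not to tell them their treatment.
2. Reword 5.5.5: treatment is open-label; the ultrasonographer and the independent joint assessor should be blinded to arm.
3. Add one eCRF field recording, per subject, whether the Week 16 joint assessor was independent and whether blinded. For subjects already assessed under the present text, record not blinded.
4. In the SAP, report Week 16 MDA and its swollen-joint component by arm and assessor status. Keep this descriptive, since status is set by site and not randomized.

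No rule on the order of recording is needed. Protocol 5.5.3 already says "After the assessment of MDA at Week 16, subjects will be assigned to one of the four treatment arms of Part 2", and that assessment uses the joint counts.

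**Cost and limits.** The change needs short amendment text, a site instruction and one data field. Sample size, test and endpoint stay as they are. Where the independent role is filled no staff are added, but an assessor who also does other procedures may need tasks reallocated. Some unblinding will occur. Not covered are sites without an independent assessor, the PASI/BSA, enthesis and patient-reported items, and subjects already assessed. Enrolment status is not stated, but SAP 4.2.2 describes randomization in the past tense, so few Week 16 visits may remain. In that case the useful parts are items 3 and 4, and naming unblinded joint counts as a limitation in the report.

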5.3.2 Drug Concentration Measurements

Blood samples for the pharmacokinetic (PK) measurement of serum ADA levels and anti-ADA antibody (AAA) concentrations will be taken at the designated visits, as specified in [Appendix C](#) only for subjects receiving adalimumab.

Collection of Samples for Serum Adalimumab Concentration and AAA Analysis

Blood samples for serum adalimumab concentration and AAA will be collected prior to dosing by venipuncture into appropriately labeled 6 mL evacuated serum collection tubes without gel separator. Sufficient blood will be collected to provide approximately 2.4 mL serum for the adalimumab and AAA assays. The central laboratory will provide supplies for sample collection, processing, storage and shipment. Please refer to the central laboratory manual for specific instructions on sample collection, processing, storage and shipment. Additional PK/AAA assays may be analyzed (where allowed by local guidelines).

